### **9.7.1. Primary Objectives**

#### **9.7.1.1. Demographic and Clinical Characteristics**

Demographic and clinical characteristics will be summarized by descriptive summary statistics for continuous variables and frequency distribution and proportions for categorical variables.

Demographic and clinical characteristics will be summarized for each of the analysis populations using the corresponding index date for treated and untreated participants as defined for each of the other study objectives.

#### **9.7.1.2. SAEs**

Frequency of all reported SAEs will be summarized and presented by Medical Dictionary for Regulatory Activities (MedDRA) system organ class (SOC)/preferred term (PT) or International Classification of Diseases (ICD), as appropriate. Event rates may also be calculated if deemed appropriate.

The analysis of SAEs will be based on data collected only after implementation of SAE reporting forms and thereby the index date will be defined as the latter of tofersen initiation, registry enrolment, or implementation of SAE forms as appropriate, and the analysis population will consist of participants who are still alive at SAE form implementation.

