## 2. LIST OF ABBREVIATIONS

Note: The following abbreviations and their definitions are considered first-use in this document. Please refer to this list for abbreviations used in this document.

AE	adverse event
ALS	amyotrophic lateral sclerosis
ALSFRS-R	Amyotrophic Lateral Sclerosis Functional Rating Scale – Revised
ALS/MND NHC	ALS/MND Natural History Consortium
BMI	body mass index
CRF	case report form
DALYS	disability adjusted life years
EMA	European Medicines Agency
EU	European Union
GVP	Good Pharmacovigilance Practice
HMA	Heads of Medicine Agency
HRQoL	health related quality of life
ICD	International Classification of Diseases
ICH	International Council for Harmonisation
LP	lumbar puncture
MA	marketing authorisation
MAH	marketing authorisation holder
MedDRA	Medical Dictionary for Regulatory Activities
MND	motor neuron disease
N/A	not applicable
PAS	post-authorisation study
PASS	post-authorisation safety study
PT	preferred term
QALYs	quality adjusted life years
RMP	risk management plan
SAE	serious adverse event
SAP	statistical analysis plan
SOC	system organ class
SOD1	superoxide dismutase 1
SOD1 -ALS	amyotrophic lateral sclerosis with a confirmed superoxide dismutase 1 mutation
TRICALS	Treatment Research Initiative to Cure ALS
UK	United Kingdom
US FDA	United States Food and Drug Administration
WHO	World Health Organization

CONFIDENTIAL

The information contained herein may not be used, disclosed, or published without the written consent of Biogen MA Inc.

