### 9.2.3. Overall Study Duration and Follow-Up

All participants with an ALS diagnosis and a confirmed *SOD1* mutation from contributing registry networks will be considered for inclusion in the study. Although this specific obligation currently has an unlimited duration, for the purpose of planning (e.g., final report), the study protocol plans for the end of data extraction for this study to be 7 years after the study start. Participants present or entering the registries during the first 5 years of the study may be included in the analyses, and the 7-year study duration allows the possibility for 2 years of follow-up for patients entering in Year 5. The expected end date may be modified based on study progress, which will be reviewed annually as part of the reassessment procedure.

Follow-up data are collected by the registry networks as part of their longitudinal data collection. All data are collected according to routine clinical practice in routine encounter-based clinic visits per the registry networks' protocols, which may occur at differing intervals, depending on the local standards for patient care. Participants are expected to be followed in the registry networks as per their respective observational

CONFIDENTIAL

The information contained herein may not be used, disclosed, or published without the written consent of Biogen MA Inc.

plans until death or loss to follow-up, regardless of tofersen treatment status. The contributing registries will not include data from participants who have withdrawn the required consents. For this study, all available data will be obtained and reported as part of the annual reassessment procedure throughout the study period.

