Data collected while a person with *SODI*-ALS is participating in an interventional clinical trial (with tofersen or any other investigational medicinal product) will be excluded since this study will focus on real-world data and the results from interventional clinical trials will be available elsewhere.

CONFIDENTIAL

The information contained herein may not be used, disclosed, or published without the written consent of Biogen MA Inc.

The analysis population and definition of index date for statistical analysis will differ by treatment status and by study objective. In general terms, index date will be the date of tofersen treatment for data from participants in the treated group or date of enrolment into the registry for data from participants in the untreated group [REDACTED]

[REDACTED] Sensitivity analyses will be performed excluding retrospectively treated participants (i.e., those who initiated tofersen treatment prior to enrolment in the registry networks).

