### **Limitations of sample size**

As *SODI*-ALS is an ultra-rare disease (< 1 case per 50,000 population) [Brown 2021], the available sample size across the 2 registry networks is expected to remain insufficient to allow hypothesis testing or subgroup analyses for this study [REDACTED]. While the protocol describes a target sample size, the target was estimated based on recent numbers of participants in the registries, which may not accurately predict the future number of *SODI*-ALS participants during the study period. To maximize the sample size of people with *SODI*-ALS, data from 2 networks of ALS disease registries are planned to be leveraged and no exclusion criteria will be applied by the study. The number of people with *SODI*-ALS included in analyses will depend on a number of factors including differences in the prevalence of *SODI*-ALS between regions/ethnic groups, availability of genetic testing, and rate of enrolment of people with *SODI*-ALS in the registries.

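### The SAE index-date rule omits the date of SOD1 confirmation, so untreated follow-up can include time in which no one later included could have died

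*Protocol*

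**What the plan says.** **Who is included.** The Protocol's abbreviation list defines SOD1-ALS as "amyotrophic lateral sclerosis with a confirmed superoxide dismutase 1 mutation". Section 9.2.3 says "All participants with an ALS diagnosis and a confirmed *SOD1* mutation from contributing registry networks will be considered for inclusion in the study". It sets no date by which confirmation must exist.

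**When the clock starts.** For SAEs, Section 9.7.1.2 states that "the index date will be defined as the latter of tofersen initiation, registry enrolment, or implementation of SAE forms as appropriate", and that "the analysis population will consist of participants who are still alive at SAE form implementation". The general rule in Section 9.7 uses "date of enrolment into the registry for data from participants in the untreated group"; the text that follows it is redacted. Neither visible rule mentions the date of mutation confirmation.

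**What is reported.** Primary endpoint 2 is the frequency of SAEs. Event rates are optional (9.7, 9.7.1.2). Death is one of the SAE criteria (Section 16). Results are stratified by treatment status, but no treated-untreated comparison is planned.

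**Genetic testing.** Section 9.9 names "availability of genetic testing" only as one factor that determines how many people are analysed. Immortal time bias is discussed only for incident versus prevalent tofersen users (9.1, 9.9).

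**The concern.** Both networks hold people with ALS in general (9.4), and only about 2% of ALS is attributed to SOD1 (7.1). A study participant is therefore someone whose genotype became known, possibly after joining the registry.

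Suppose a person enrols in January, is confirmed in July and stays untreated. With SAE forms already in place, follow-up counts from January. An identical person who dies untested in April never enters. January to July is then time that only survivors can contribute.

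The plan already handles one entry condition in this way, by requiring participants to be alive at SAE-form launch. It does not do so for the condition that defines the study population. Treated participants should be largely spared, because the indication presupposes a known SOD1 mutation. At stake is whether an untreated death or fatal-SAE rate, if calculated, describes the people it claims to describe.

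**Working it through.** **1. The plan's own figures.** 25 per year × 5 years = 125 cases; 125 × 0.40 = 50 treated; 50 × 2 years = 100 treated person-years. The reference rate is 12 / 368.83 = 0.0325, stated as 0.033. With 4 events in 100 person-years, exact Poisson limits are 0.0109 to 0.1024, as in Table 3; the other four rows also reproduce. All of this concerns treated participants, so the point leaves it unchanged.

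**2. Untreated person-time.** By the same assumptions, 125 × 0.60 = 75 untreated people and about 75 × 2 = 150 person-years (using the 2-year median as if it were a mean). If a share of those included were confirmed after index by a given lag, the time concerned is 75 × share × lag:
- none confirmed late: 0
- 10% late by 0.25 years: 1.9 person-years (about 1% of 150)
- 50% late by 1 year: 37.5 person-years (25% of 150)

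The documents give neither the share nor the lag.

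**3. Effect on a death rate (illustration).** Assumptions, not taken from the plan: constant death hazard h, follow-up to τ years, everyone's clock starting at enrolment, and a share f of SOD1 cases confirmed d years later, with those who die first never included. Per source case:
- confirmed at index: deaths A = (1 − f)(1 − e^(−hτ)); person-years A/h
- confirmed late: deaths B = f·e^(−hd)·(1 − e^(−h(τ−d))); person-years after confirmation B/h; person-years before confirmation C = f·e^(−hd)·d
- rate under the rule as written: (A + B) / (A/h + B/h + C)
- rate with time starting at confirmation: (A + B) / (A/h + B/h) = h

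Example with a 2-year median (h = ln 2 / 2 = 0.3466), τ = 5, f = 0.25, d = 0.5: A = 0.6174, A/h = 1.7815; B = 0.1660, B/h = 0.4791; C = 0.25 × 0.8409 × 0.5 = 0.1051. As written: 0.7834 / 2.3657 = 0.331. From confirmation: 0.7834 / 2.2606 = 0.347.

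| Late share | Lag 3 months | Lag 6 months | Lag 12 months |
|---|---|---|---|
| 0% | 0.347 (0%) | 0.347 (0%) | 0.347 (0%) |
| 25% | 0.338 (−2.4%) | 0.331 (−4.4%) | 0.320 (−7.6%) |
| 50% | 0.330 (−4.8%) | 0.316 (−8.9%) | 0.293 (−15.3%) |

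**4. Sensitivity.** With the 2.3-year median survival of Section 7.1 (h = 0.301; its time origin is not stated) and a 2-year horizon, the understatement is 1.5% (10% late, 3 months), 7.2% (25%, 6 months) and 25.7% (50%, 12 months). A shorter horizon enlarges it.

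**5. What does not move.** A person who dies before confirmation is absent whichever start date is used. The number included, the number of fatal SAEs and the crude proportion who die are therefore the same under either rule. Only quantities with person-time in the denominator change.

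**The case against.** The strongest reply is that no late-confirmed participant has been shown to exist. SOD1-ALS is defined as confirmed, and Section 9.5 speaks of incident SOD1-ALS cases enrolling, which can be read as confirmed at enrolment. A reader might infer that the untreated stratum does contain guaranteed survival time. The documents do not support that; they support only that nothing visible prevents it. Confirmation after death would not create such time either.

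A reader might also infer that all untreated SAE rates are too low. Only death is impossible in the gap; non-fatal SAEs can occur and be recorded. Nor is a treated-untreated contrast distorted, since none is planned and Section 9.9 calls such comparisons invalid. Describing baseline characteristics at enrolment is a legitimate choice.

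The illustration does not model the SAE rule exactly. It counts everyone from enrolment, whereas prevalent cases already confirmed at SAE-form launch would contribute no such time.

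Redaction and deferral to the SAP carry less weight. The redacted text follows the general rule in 9.7, so that rule can be judged only as far as it is visible. The SAE rule in 9.7.1.2 is unredacted and names its three dates, though qualified by a phrase allowing for what is appropriate. What 9.7 expressly defers about index dates is the effect of excluding clinical-trial data.

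**Conclusion.** The point holds as a conditional flaw in a stated rule. Inclusion depends on a confirmed mutation, the SAE index date ignores when that happened, and nothing visible requires confirmation by index. Any untreated participant confirmed in life after index adds death-free time to the denominator.

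If event rates are calculated, the untreated death and fatal-SAE rates would then be too low. The amount cannot be estimated from the documents. It is nil if all are confirmed by index, and about 2% to 15% under the assumed 25% to 50% late, 3 to 12 month lag, 2-year median survival and 5-year cap. These shares and lags are assumptions chosen to show a range. The practical weight is modest: the study is descriptive, rates are optional, and the treated target and precision are untouched.

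**What to change.** In 9.7.1.2, and in the general untreated rule of 9.7 as far as it is visible, state that for any person-time rate at-risk time starts at the latest of:
- registry enrolment
- SOD1 confirmation, or the first record of SOD1 status if the test date is not held
- SAE-form implementation
- tofersen initiation, if treated

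Report the number of participants confirmed after enrolment or form launch and the person-time concerned. List separately any SAEs recorded before confirmation, so that they are not lost. Counts and baseline tables can stay as planned.

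The cost is one date variable from each network. Section 9.3 lists mutation type but no test date, and Annex 4 lists none either, so availability must be checked before extraction starts. A first-record date may partly reflect when data were entered. The rates lose a little untreated person-time and the non-fatal SAEs that precede confirmation.

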### **9.7.2. Secondary Objectives**

#### **9.7.2.1. New Comorbid Conditions, Pregnancy and Pregnancy Outcome**

Frequency of new comorbid conditions, pregnancy and pregnancy outcomes will be reported. Event rates may also be calculated if deemed appropriate.

#### **9.7.2.2. Treatment Discontinuation**

Summary statistics of the duration of treatment use and prescribed dosing frequency will be provided among people with *SOD1*-ALS receiving tofersen. Frequency and proportion of participants with treatment discontinuation will be reported. Reported reason for treatment discontinuation will be tabulated.

CONFIDENTIAL

The information contained herein may not be used, disclosed, or published without the written consent of Biogen MA Inc.

[REDACTED]

[REDACTED]

[REDACTED]

[REDACTED]

[REDACTED]

[REDACTED]

[REDACTED]

## 9.8. Quality Control

This study will use data from 2 existing networks of ALS disease registries. All data in the registry networks are collected according to routine clinic visits. Each registry network will use its own standard operating procedures, internal policies, or process guidance. The registry processes may include rules for data entry, data storage, methods to maintain and archive project and study documents, quality-control procedures for programming, standards for writing analysis plans, review of analysis programs and study documents by senior staff as well as internal audits if applicable.

The level of completeness for study variables will be monitored in each registry network throughout the course of the study. Biogen may work with the registry networks on supplementing their processes on an as-needed basis, and in accordance with registry governance.

The registry networks were selected for this study based on feasibility assessments, including review of protocols, processes, and relevant agreements between Biogen and the data source owners. Biogen will work with the registries to develop methods to enhance the quality of data and reporting for this protocol in line with guidances, where applicable (e.g., EMA data quality framework for EU medicines regulation [[EMA 2023](#)]).

### 9.8.1. Quality Assurance

Quality control procedures will be implemented at each stage of data handling. Prior to data delivery to Biogen or a third party on behalf of Biogen, the data holders will collect and manage data according to their own standards and in alignment with contracted agreements with Biogen. Quality control on the deliverables will be performed by Biogen or a third party acting on behalf of Biogen. Data anomalies will be communicated by Biogen to the registries for clarification and resolution, as appropriate. Any data entries that need to be resolved will be communicated by the registries to the impacted sites and corrected at site and central registry levels.

CONFIDENTIAL

The information contained herein may not be used, disclosed, or published without the written consent of Biogen MA Inc.

## 9.9. Limitations of the Research Methods

Although measures will be taken to ensure that the study is methodologically robust, certain limitations should be acknowledged, and all results should be interpreted considering these limitations.

### Limitations of study setting and observational design

While a registry-based study allows data extraction from a broad population of people with *SODI*-ALS, there are some limitations associated with this approach. Specifically, the data collected by the registry networks reflect local regulations and clinical practice, as well as registry governance and processes. This may result in some heterogeneity and inconsistency across sites and associated data quality concerns (e.g., missingness or loss to follow-up patterns). As the data in the registry networks are collected according to routine clinical practice, the frequency of clinical assessments, such as the ALSFRS-R, may vary by region or clinical practice.

Registry-based studies may have potential selection bias and uncertain generalizability. The registries might not represent the population of all people with *SODI*-ALS. For example, people with *SODI*-ALS living in more rural areas might be under-represented. However, participants in ALS/MND NHC have been shown to be more heterogeneous compared to anonymized clinical trial data from the Pooled Resource Open-Access ALS Clinical Trials database [Berger 2023].

As the registry networks are of observational design, treatment assignment is non-random. There will likely be systematic differences in the demographic and clinical characteristics, follow-up, and clinical outcomes between tofersen treated and untreated participants that preclude comparisons between tofersen treated and untreated participants. Statistical approaches to address these differences like matching require larger sample sizes than feasible for studies of ultra-rare diseases like *SODI*-ALS (< 1 case per 50,000 population) [Brown 2021]. Therefore, valid comparisons cannot be drawn between the tofersen treated and untreated participants in this study. The analysis is focused on descriptive statistics, and the study includes untreated participants with *SODI*-ALS to help improve understanding of tofersen drug utilization in the context of this ultra-rare disease.

This study will include data from both prevalent and incident tofersen users. The assessment of incident drug users is a key study design feature to avoid immortal time bias [Suissa 2008] and depletion of susceptibles in real-world evidence studies [Moride and Abenheim 1994]. However, in the case of ultra rare diseases like *SODI*-ALS, the inclusion of participants with prevalent *SODI*-ALS, including tofersen users at the start of data extraction, will allow the collection of as much data as possible. The potential biases resulting from inclusion of prevalent users is acknowledged, and the analysis will take these potential biases into consideration (e.g., reporting results separately for prevalent and incident tofersen users if deemed appropriate). The safety profile of tofersen will be characterized through a review of the SAE data reported from individual participants during the study with a particular focus on the relationship assessment recorded on the SAE forms, temporal relationship of SAEs to tofersen dosing, the

CONFIDENTIAL

The information contained herein may not be used, disclosed, or published without the written consent of Biogen MA Inc.

consistency of SAE reports with tofersen clinical trial data and published literature, biologic plausibility, and confounding factors including known comorbidities of ALS.

### **Limitations of missing data**

Missing reporting on exposure, covariates, and outcomes has the potential for misclassification of these variables. All efforts will be made by the registry networks to collect data as completely as possible. The data capture platforms of both registry networks have systems and data management processes that highlight and query for missing data in an attempt to minimize missingness. However, missing data or partial dates could still occur. To address this, an additional category of ‘missing’ will be added to account for missing data in analyses and partial dates will be imputed for analysis purposes as detailed in the SAP. Further, there is potential for unmeasured confounding (unmeasured third variable influencing the exposure and outcome). All analyses will be descriptive and there will be no assessment of treatment effects.

### **Limitations of sample size**

As *SODI*-ALS is an ultra-rare disease (< 1 case per 50,000 population) [Brown 2021], the available sample size across the 2 registry networks is expected to remain insufficient to allow hypothesis testing or subgroup analyses for this study [REDACTED]. While the protocol describes a target sample size, the target was estimated based on recent numbers of participants in the registries, which may not accurately predict the future number of *SODI*-ALS participants during the study period. To maximize the sample size of people with *SODI*-ALS, data from 2 networks of ALS disease registries are planned to be leveraged and no exclusion criteria will be applied by the study. The number of people with *SODI*-ALS included in analyses will depend on a number of factors including differences in the prevalence of *SODI*-ALS between regions/ethnic groups, availability of genetic testing, and rate of enrolment of people with *SODI*-ALS in the registries.

## **9.10. Other Aspects**

### **9.10.1. Study Funding**

Biogen is the MAH of Qalsody, and as the sponsor of this study is funding the secondary data analysis of registry data. All financial details are provided in the separate contracts between the institutions, Investigators, and Biogen.

CONFIDENTIAL

The information contained herein may not be used, disclosed, or published without the written consent of Biogen MA Inc.

## **10. PROTECTION OF HUMAN PARTICIPANTS**

Biogen must comply with this protocol and applicable International Conference on Harmonisation and GVP guidelines and conduct the study according to local regulations.

This study will be performed in alignment with the ethical principles outlined in the Declaration of Helsinki.

